7.9.10 Exploratory biomarker research and pharmacogenetic study

The number of patients who will agree to participate in the exploratory biomarker and genetic research is unknown. It is therefore not possible to establish whether sufficient data will be collected to allow a formal statistical evaluation or whether only descriptive statistics will be generated. The exploratory biomarker study results will not be included in CSR.

7.10 Publication policy

This policy applies to Spain.

All information concerning the product as well as any matter concerning the operation of the Sponsor, such as clinical indications for the drug, its formula, methods of manufacture and other scientific data relating to it, that have been provided by the Sponsor and are unpublished, are confidential and must remain the sole property of the Sponsor. The Investigator will agree to use the information only for the purposes of carrying out this study and for no other purpose unless prior written permission from the Sponsor is obtained.

Samples and/or data will be processed centrally, and the results will be sent electronically to the Sponsor or designated CRO. Data that will be processed centrally includes central imaging review data (CT/MRI), central ECG data and centrally analyzed laboratory data including PK and blood/tumor biomarker samples.

The Sponsor has full ownership of the original eCRFs completed as part of the study.

By signing the clinical study protocol, the Investigator agrees that the results of the study may be used for the purposes of national and international registration, publication, and information for medical and pharmaceutical professionals. The authorities will be notified of the Investigator's name, address, qualifications, and extent of involvement.

After conclusion of the clinical trial, an integrated clinical and statistical study report will be prepared by the Sponsor or designee. As soon as possible and no later than one year, the trial results must be entered in European Clinical Trials Database clinicaltrialsregister.eu.

All materials, documents and information supplied by the Sponsor to the Investigator, and all materials, documents and information prepared or developed in the course of the study to be performed under this protocol, shall be the sole and exclusive property of the Sponsor. Subject to obligations of confidentiality, the Investigator reserves the right to publish only the results of the work performed pursuant to this protocol, provided, however, that the Investigator provides an authorized representative of the Sponsor with a copy of any proposed publication for review and comment at least 45 days in advance of its submission for publication. In addition, if requested, the Investigator will withhold publication an additional 90 days to allow for filing a

Date: July 24,2023

patent application or taking such other measures as Sponsor deems appropriate to establish and preserve its proprietary rights.

It is agreed that, consistent with scientific standards, publication of the results of the study shall be made only as part of a publication of the results obtained by all sites performing the protocol.

8.2 Overdose

There are no data on overdosing since this is the first study in humans with DZD9008. There is no definition of what constitutes an overdose. There is no known antidote. Investigators will be advised that any patient who receives a higher dose than that intended should be monitored closely, managed with appropriate supportive care and followed up expectantly.

Such overdoses should be recorded as follows:

Date: July 24,2023

- An overdose with associated AEs/SAEs is recorded as the AE diagnosis/symptoms on the relevant AE/SAE modules in the CRF and on the overdose CRF module.
- An overdose with no associated symptoms is only reported on the overdose CRF module.

If an overdose occurs in the course of the study, then investigators or other site personnel inform appropriate Dizal representatives immediately, or no later than 24 hours of when he or she becomes aware of it.

The designated Dizal representative works with the investigator to ensure that all relevant information is provided to the Dizal Patient Safety team or representatives.

For overdoses associated with an SAE, standard reporting timelines apply, see Section 6.4.4.

8.3 Pregnancy

All pregnancies and their subsequent outcome (spontaneous miscarriage, elective termination, ectopic pregnancy, normal birth or congenital abnormality) should be reported to Dizal using the appropriate forms.

8.3.1 Maternal exposure

If a patient becomes pregnant during the course of the study, investigational product should be discontinued immediately.

Pregnancy itself is not regarded as an adverse event unless there is a suspicion that the investigational product under study may have interfered with the effectiveness of a contraceptive medication. Congenital abnormalities/birth defects and spontaneous miscarriages should be reported and handled as SAEs. Elective abortions without complications should not be handled as AEs. The outcome of a pregnancy should be followed up and documented even if the patient was withdrawn from the study.

If a pregnancy occurs during exposure to investigational product or in the 28 days after discontinuing investigational product, then investigators or other site personnel inform appropriate Dizal representatives immediately, or no later than 24 hours of when he or she becomes aware of it.

The designated Dizal representative works with the investigator to ensure that all relevant information is provided to the Dizal Patient Safety team within 1 or 5 days for SAEs, (see Section 6.4.4) and within 28 days for all other pregnancies.

The same timelines apply when outcome information is available.

8.3.2 Paternal exposure

Pregnancy of a patient's partner is not considered to be an adverse event. However, any conception occurring from the date of dosing until 16 weeks after dosing should be reported to Dizal and followed up for its outcome.

Date: July 24,2023

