4.3 Restrictions

The following restrictions apply while the patient is receiving study treatment for the specified time before and after:

- 1. Male patients with female partners of child-bearing potential should be willing to use barrier contraceptives (i.e., by use of condoms), during their participation in this study and for 6 months following the last dose of the study drug. Patients should avoid procreation for 6 months after completion of trial treatment. Male patients must refrain from donating sperm during their participation in the study and at least for 6 months after the last treatment. If male patients wish to father children, they should be advised to arrange for freezing of sperm samples prior to the start of study treatment.
- 2. Females of child-bearing potential should use reliable methods of contraception from the time of screening until 6 weeks after discontinuation. Acceptable methods of contraception include total sexual abstinence, tubal ligation, hormonal contraceptives that are not prone to drug-drug interactions (IUS Levonorgestrel Intra Uterine System (Mirena), Medroxyprogesterone injections (Depo-Provera), copper-banded intrauterine devices and vasectomized partner. All hormonal methods of contraception should be used in combination with the use of a condom by their male sexual partner for intercourse. Female patients should not be breast feeding and must have a negative pregnancy test prior to start dosing if of child-bearing potential or must have evidence of non-child-bearing potential by fulfilling one of the following criteria at screening:
 - Post-menopausal defined as aged more than 50 years and amenorrhea for at least 12 months following cessation of all exogenous hormonal treatment.
 - Documentation of irreversible surgical sterilization by hysterectomy, bilateral oophorectomy or bilateral salpingectomy but not tubal ligation.

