- Higher incidence of dose reduction and interruption occurred at 400 mg cohort was observed as compared to 200 mg and 300 mg cohort, which presumably led to lower clinical efficacy at the 400 mg cohort (ORR 25% at 400 mg). As the doses of 100 mg or above demonstrated clinical activity, and 200 mg or 300 mg is expected to overcome PK variability of DZD9008 to achieve pharmacological relevant exposure required from different subtypes of Exon20ins, thus selecting both 200 mg and 300 mg is appropriate to further evaluate DZD9008 dose optimization for the phase 2 pivotal study.
- DZD9008 elimination half-life is approximately 50 hours following a single dose across the doses investigated, which supports the once daily dosing regimen of DZD9008 in clinical development.

Ethnic sensitivity

 Based on the available data, no obvious difference in safety, PK and anti-tumor efficacy of DZD9008 was observed between Asian and White patients across different regions/countries. Therefore, Dizal believes that the use of same dose and schedule across different regions and countries is appropriate.

Patients enrolled to Part B will receive repeated dosing of DZD9008 at 200 mg or 300 mg once daily. Following review and approval form IEC/IRB and/or local regulatory authority (as applicable) on the optimal RP2D selction, eligible patients can be enrolled into the optimal RP2D cohort. The ongoing patients previously randomized to the suboptimal Part B dose cohort can maintain the same dose level, or shift to receive the optimal RP2D, if judged by the investigator that it is of the best clinical benefit to patients and re-consent is needed (see section 5.1). DZD9008 will be administrated with food as dosing with high fat food in Part A showed limited effect on DZD9008 exposure. Patients with prior therapy may be stratified into subcohorts when data is analyzed.

Patients will receive repeated daily dosing of DZD9008 until disease progression, intolerable AEs, discontinuation criteria have met or withdrawal of consent.

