6.3.6 Follow up

6.3.6.1 Safety follow up

A post study assessment will be performed at the time investigational product is permanently discontinued.

As a minimum, telephone contact should be made with the patient for 28 days following the discontinuation of DZD9008 to collect new AEs and follow up on any ongoing AEs and concomitant medications (including any subsequent cancer therapy). Refer to Section 6.4.3 for full details on AE recordings during follow-up.

Beyond the 28 day follow up, only ongoing AEs or study procedure-related SAE should be collected. Any SAE will be followed to resolution where possible.

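### The 16-week window for reporting partner conceptions names no dose and, counted from the last dose, ends about 10 weeks before the men's 6-month contraception period

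*Protocol*

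**What the plan says.** Protocol section 8.3.2 (Paternal exposure) states that pregnancy of a patient's "partner is not considered to be an adverse event". It then asks that "any conception occurring from the date of dosing until 16 weeks after dosing should be reported to Dizal" and that the outcome be followed. It does not say whether the 16 weeks run from the first dose, the last dose or some other dose. Section 5.1.4 makes clear that dosing is not a single event: "Patients will receive repeated daily dosing of DZD9008 until disease progression".

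Section 4.3 item 1 sets the men's restrictions, and all three last longer than 16 weeks:
- Barrier contraception during participation and "for 6 months following the last dose of the study drug".
- No fathering of a child over the same length of time, counted from the end of treatment.
- No sperm donation while on the study or for a minimum of 6 months once treatment has ended.

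Section 8.3, the parent of 8.3.2, is broader: "All pregnancies and their subsequent outcome (spontaneous miscarriage, elective termination, ectopic pregnancy, normal birth or congenital abnormality) should be reported to Dizal". It has no time limit and does not mention partners.

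On safety collection after treatment, section 6.3.6.1 says: "Beyond the 28 day follow up, only ongoing AEs or study procedure-related SAE should be collected".

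**The concern.** There are two separate weaknesses in 8.3.2. The start of the 16 weeks is undefined. And on the reading most favourable to the plan, the last dose, the reporting duty lapses while the man is still under instruction not to conceive. The sponsor chose 6 months as the period in which paternal exposure calls for caution. A conception in that period is the kind whose outcome one would want to know, yet the only clause that sets a window for partner conceptions stops short of it, and no reason is given.

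At stake is the completeness of safety reporting. A site that works from the specific clause rather than the general one could properly conclude that a conception at, say, week 20 after the last dose need not be reported. Adverse event collection would not reliably pick it up, because a partner's pregnancy is declared not to be an adverse event and collection narrows sharply after the 28-day follow-up.

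**Working it through.** **Inputs**
- Reporting window for partner conceptions: 16 weeks, dose not named (protocol 8.3.2).
- Men's contraception, procreation and sperm-donation restrictions: 6 months after the last dose or end of treatment (protocol 4.3 item 1).
- Month length: 30.4375 days, the conversion factor the SAP uses (for example in SAP 4.1).
- Cycle length in Part B: 21 days (protocol Table 14).
- Contacts after treatment in Part B: every 6 weeks after progression or withdrawal from treatment (protocol 6.3.6.3 and the survival-status footnote to Table 14).

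**Last-dose reading**
- Reporting window: 16 × 7 = 112 days.
- Men's restriction period: 6 × 30.4375 = 182.6 days; 182.6 / 7 = 26.1 weeks.
- Gap: 182.6 − 112 = 70.6 days; 70.6 / 7 = 10.1 weeks.
- Share of the restriction period outside the reporting window: 70.6 / 182.6 = 38.7%.
- Calendar check: six consecutive calendar months last 181 to 184 days, so the gap is 181 − 112 = 69 to 184 − 112 = 72 days, that is 9.9 to 10.3 weeks.

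**First-dose reading**
- 112 / 21 = 5.3, so the window would close during Cycle 6. Part B plans pharmacokinetic sampling to Cycle 11 (protocol Tables 8 and 9), and the exposure categories in SAP 5.5 extend beyond 12 months. A man could therefore still be taking the drug daily when the reporting window had closed. The shortfall would be larger than 10 weeks.

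**Existing contacts that could carry the longer window (Part B)**
- Counted from withdrawal from treatment, 6-weekly contacts fall at weeks 6, 12, 18, 24 and 30. Those after week 16 and no later than week 26.1 are weeks 18 and 24.
- Survival follow-up is specified for the Part B cohorts only, so Part A has no equivalent.

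**The case against.** The strongest reply is that section 8.3 already requires all pregnancies to be reported, that 8.3.2 sits beneath it, and that nothing in 8.3.2 says later conceptions may be ignored. On that view there is no gap, only a more specific instruction inside a general one. This is why the point is not put as a contradiction. But 8.3 does not name partners, 8.3.2 is the clause headed for paternal exposure, and if 8.3 applied to partners without limit, the 16-week end date would have no function.

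Second, a reporting window need not equal a contraception window. The women's provisions also differ: contraception until 6 weeks after discontinuation (4.3 item 2), against pregnancies during exposure or in the 28 days after it in 8.3.1. That is true as a principle. However, the 28 days in 8.3.1 set a 24-hour notification duty, and 8.3.1 separately asks for the outcome of a pregnancy to be followed even after withdrawal. In 8.3.2 the single window governs both the report and the follow-up.

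Third, the half-life is about 50 hours, so 16 weeks is 112 × 24 / 50 = about 54 half-lives, and section 2.3.4 reports no evidence of genotoxicity. These facts suggest that the biological risk late in the gap is low. They would bear equally on the 6-month restriction, which the sponsor nevertheless imposed.

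Fourth, section 6.4.3.2 asks investigators to notify the sponsor of a possibly drug-related serious event learned of after a patient has completed the study, and a birth defect is a seriousness criterion in 6.4.2. Whether this reaches a partner's child is arguable. At best it catches a bad outcome that someone happens to report and attribute to the drug; it does not ask for the conception to be reported or followed.

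Finally, the pregnancy report forms and consent text are not in the documents available, so what sites and men are told about timing in practice cannot be checked.

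**Conclusion.** The concern holds, as a minor one. Section 8.3.2 leaves the dose unnamed. Taking it as the last dose, the partner-conception window ends about 71 days (69 to 72 by calendar), or about 10 weeks, before the men's restrictions in 4.3 item 1 end. That is about 39% of the 6 months. Taking it as the first dose, the shortfall is greater and the window can close during treatment.

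The practical consequence depends on a site following 8.3.2 rather than the broader 8.3. The number of conceptions concerned is likely to be very small, although the documents give no figure. No endpoint, analysis set, error rate or sample size is touched.

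**What to change.** In section 8.3.2, define the window as *from the first dose until 6 months after the last dose of DZD9008*. This names the dose and matches 4.3 item 1 in one edit. Sections 8.3 and 8.3.1 can stay as they are.

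The cost is one wording change at the next amendment and at most a few extra reports. No new visit is needed: in Part B the existing contacts at about weeks 18 and 24 after withdrawal from treatment fall in the added period and could be used to ask. Part A has no survival follow-up, so there the longer window would rely on men telling the site.

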Demography & baseline characteristics	X													6.3.1
Medical/surgical history	×													6.3.1
Inclusion/exclusion criteria	×													4.1 & 4.2
Physical examination	×	×						×			X	X		6.3.2
ECOG performance status	X	×						×			X	X		6.3.2
Brain MRI	X													4.1
Pregnancy test (premenopausal females only) ^c	X											X		6.3.4
Ophthalmologic assessment i	×											×		6.3.5
Archival tumor tissue or fresh biopsy collection (mutation confirmation)	X													6.6.2
Vital signs	X	X	X					×	X	X	X	X		6.3.3
Height	X													6.3.3
Weight	X	×						X			X	X		6.3.3
ECG	X	X	X					X	×	X	Х	X		6.3.5
Clinical chemistry/ Hematology/Urinalysis	X	×						×	×	×	×	×		6.3.4
Echocardiogram/MUGA®	X								on Cycle	3 Day	on Cycle 3 Day1, then every 6 weeks	6 weeks		6.3.5

Assessment	Screen		Day	Cycle 0 s (cycle 0=	Cycle 0 Days (cycle 0=8 days)	ays)		Cycle	Cycle 1 (28 days)	days)	Cycle 2 (21 days) onwards	Discontinuat ion	28 day follow up	Details in section
Day	-28~-1	1 ^h	2	3	4	9	∞	1 _h	œ œ	15a	1 _b			
Lung function test (LFT) e	X								on Cy	cle 3 Da	on Cycle 3 Day1, then every 6 weeks	6 weeks		6.3.5.3
HBV, HCV, HIV, COVID-19 ^d	X													4.2
APTT/INR	X	×						×	×	×	×	X		6.3.4
Blood PK samples (including metabolites)		*X	X	X	X	X	×	X	×	X	X**			6.5.1
PK Urine (including metabolites)											X#			6.5.1
4-β hydroxycholesterol / total cholesterol		X						X	X	X	X (C2 only)			6.5.3
Dose with DZD9008		×						\		X (dai	←X (daily dosing)→	↑		5.1
Blood samples for ctDNA & Biomarkers (optional)	X	×						×	×	×	X (C2D1-Co	X (C2D1-C6D1 and continuous every even cycle D1 until disease progression)	ous every ogression)	6.6.2.3
RECIST assessments ^f	X							~) uo	Sycle 3 I)ay1, then every 6 progression→	←on Cycle 3 Day1, then every 6 weeks until disease progression →	isease	6.8.1
Concomitant medication	→											←		4.3.1
Adverse events ^g	→											^		6.4
	., .,	.,	٠,				11							

^{#:} Multiple time point for PK sampling. Hospitalization can be allowed for out of business time PK collection. *: Day 1 of Cycle 2, 3, 4 and 5

 $[\]pm 1$ day visit window is allowed for C1D8 & D15. ä.

All study visits from Cycle 2 Day 1 onwards may be performed within a visit window of ± 2 days. Ъ.

Pregnancy test needs to be within 3 days of the first dosing. ပ်

HBV/HCV/HIV/COVID-19 tests can be done based on local practice. ن

Echo/MUGA and LFT at baseline needs to be done within 14 days of the first dosing. e.

CT is preferred. Same scan modality is required to use for tumor scan and RECIST assessment from baseline till follow up for one patient. Please refer to Appendix F of CSP about the details of RECIST assessment. £.

- AE will be collected from first dosing of DZD9008; SAE is required to be collected from inform consent ás
- h. For C0D1 and C1D1, -1 day window is allowed for laboratory safety testing and physical examination
- Eye examination includes: Visual acuity, Pupils, Intraocular pressure, External examination, Slit-lamp examination, and Fundoscopic examination (pupil dilate is not required) and others if clinically indicated.

Table 12 Study Plan of Food Effect Cohort (Part A, food effect)

Assessment	Screen				*	Days	Cycle 0	Cycle 0 Days (cycle 0=16 days)	ó days	~				C [5]	Cycle 1 (21 days)		Cycles 2 (21 days) onwards	Disconti nuation	28-day Follow Up	Details in section
Day		1 ^h	2	3	4	9	8	6	10	11	12	14	16	1 h	8a	15ª	1^{b}			
Informed consent	X																			4.1.1
Demography & baseline characteristics	X																			6.3.1
Medical/surgical history	X																			6.3.1
Inclusion/exclusion criteria	X																			4.1 & 4.2
Physical examination	X	X						X						X			X	X		6.3.2
ECOG performance status	X	X						X						X			X	X		6.3.2
Brain MRI or contrast- enhanced CT	X																			4.1
Pregnancy test (premenopausal females only) ^c	X																	X		6.3.4
Ophthalmologic assessment	X																	X		6.3.5.4
Archival tumor tissue or fresh biopsy (mutation confirmation)	X																			6.6.2
Vital signs	X	X						X						X	X	X	X	X		6.3.3
Height	X																			6.3.3
Weight	X	X												X			X			6.3.3
ECG	X	X						X						X	X	X	X	X		6.3.5
HBV, HCV, HIV, COVID- 19 ^d	×																			4.2

Drug Substance: DZD9008 Protocol No.: DZ2019E0001 Edition Number: 12.0 Date: July 24,2023 Clinical Study Protocol

Assessment	Screen				*	Days (Cycle 0 (cycle 0=	e 0 0=16	Cycle 0 Days (cycle 0=16 days)					C ₅	Cycle 1 (21 days)		Cycles 2 (21 days) onwards	Disconti	28-day Follow Up	Details in section
Day		ųΙ	2	3	4	9	∞	6	10	11	12	14	16	1 h	8a 1:	15ª	1^{b}			
Clinical chemistry/ Hematology/Urinalysis	X	X						×						×	X	×	Х	X		6.3.4
APTT/INR	X	X						X						X	$X \mid X$	X	X	X		6.3.4
Echocardiogram/MUGA°	X													On C	ycle 3	Day 1,	On Cycle 3 Day 1, then every 6 weeks	6 weeks		6.3.5.2
Lung function test (LFT) e	X													On C	ycle 3	Day 1,	On Cycle 3 Day 1, then every 6 weeks	6 weeks		6.3.5.3
PK blood samples		X #	X	X	X	X	X	*X	X	X	X	X	X				χi			6.5.1.1
Blood sample for ctDNA & Biomarkers (optional)	X	X												×	×	×	ζ (C2D1-C even c	2D1-C6D1 and continuous e even cycle D1 until disease progression)	X (C2D1-C6D1 and continuous every even cycle D1 until disease progression)	6.6.2.3
RECIST assessments ^f	X												-	On C3	cle 3 I)ay 1,	then every	6 weeks unt	On Cycle 3 Day 1, then every 6 weeks until progression	6.8.1
Dose with DZD9008		X						X						·	X	(daily	\leftarrow X (daily dosing)	*		5.1.1
Concomitant medication			V	····	!!												←	←		4.3.1
Adverse events g			\downarrow														<	+		6.4

^{#:} Multiple time point for PK sampling. Hospitalization can be allowed for out of business time PK collection. * Treatment date might be update in light of emerging human PK data

ပ

^{±1} day visit window is allowed for C1D8 & D15.

All study visits from Cycle 2 Day 1 onwards may be performed within a visit window of ± 2 days. Ъ.

Pregnancy test needs to be within 3 days of the first dosing.

HBV/HCV/HIV/COVID-19 tests can be done based on local practice. Ġ.

Echo/MUGA and LFT at baseline needs to be done within 14 days of the first dosing. Ġ.

CT is preferred. Same scan modality is required to use for tumor scan and RECIST assessment from baseline till follow up for one patient. Please refer to Appendix F of CSP about the details of RECIST assessment.

AE will be collected from first dosing of DZD9008; SAE is required to be collected from inform consent ы́

- For C0D1 and C1D1, -1 day window is allowed for laboratory safety testing and physical examination Ъ.
- Eye examination includes: Visual acuity, Pupils, Intraocular pressure, External examination, Slit-lamp examination, and Fundoscopic examination (pupil dilate is not required) and others if clinically indicated. . **.:**
- j. Pre-dose on Cycle 2 day 1.

Table 13 Study Plan of Part A Dose Expansion

Assessment	Screen)	Cycle 1 (21 days)		Cycle 2 (21 days) onwards	Discontinuation	28-day follow up	Details in section
Day	-28 to -1	1 h	8 _a	15ª	1^{b}			
Informed consent	X							4.1.1
Demography & baseline characteristics	X							6.3.1
Medical/surgical history	X							6.3.1
Inclusion/exclusion criteria	×							4.1 & 4.2
Physical examination	X	X			X	X		6.3.2
ECOG performance status	X	X			X	X		6.3.2
Brain MRI or contrast-enhanced CT	X							4.1
Pregnancy test (premenopausal females only) ^c	X					X		6.3.4
Ophthalmology assessment i	X					X		6.3.5.4
Archival tumor tissue or fresh biopsy (mutation confirmation)	X							6.6.2
Vital signs	X	X	X	X	X	X		6.3.3
Height	X							6.3.3
Weight	X	X			X	X		6.3.3
ECG	X	X	X	X	X	X		6.3.5
Clinical chemistry/ Hematology/Urinalysis	×	×	×	×	X	X		6.3.4
HBV/HCV/HIV/COVID-19 ^d	×							4.2

Assessment	Screen)	Cycle 1 (21 days)		Cycle 2 (21 days) onwards	Discontinuation	28-day follow up	Details in section
Day	-28 to -1	1 h	в8	15 ^a	1^{b}			
APTT/INR	×	×	×	×	×	×		6.3.4
Echocardiogram/MUGA °	×	V		On (←On Cycle 3 Day 1, then every 6 weeks→	↑		6.3.5.2
Lung function test (LFT) °	×	V		On	← On Cycle 3 Day 1, then every 6 weeks	↑		6.3.5.3
PRO-CTCAE and FACIT GP5 questions		×	X	X	Weekly until the end of cycle 6, then on day 1 of each cycle	X		6.9.2 & 6.9.3
PK blood samples		*X	X	X	$_{*}$			6.5.1.2
Blood sample for ctDNA & exploratory Biomarkers (optional)	Х	X	X	X	X (C2D1-C6D1 and continuous every even cycle D1 until disease progression)	very even cycle D1 until	l disease	6.6.2
RECIST assessments ^f	×		↓		\leftarrow On Cycle 3 Day 1, then every 6 weeks	eks		6.8.1
Dose with DZD9008				→	←X (daily dosing)X	^		5.1.2
Concomitant medication	*				X	←		4.3.1
Adverse events 8	*				←	^		6.4

#: multiple time point for PK sampling. Hospitalization can be allowed for out of business time PK collection.

- a. ±1-day visit window is allowed for C1D8 & D15.
- b. All study visits from Cycle 2 Day 1 onwards may be performed within a visit window of \pm 2 days.
- c. Pregnancy test needs to be within 7 days of the first dosing.
- d. HBV/HCV/HIV/COVID-19 test can be done based on local practice.
- e. Echo/MUGA and LFT needs to be done within 14 days of the first dosing.
- CT is preferred. Same scan modality is required to use for tumor scan and RECIST assessment from baseline till follow up for one patient. Please refer to Appendix F of CSP about the details of RECIST assessment. ij
- AE will be collected from the first dosing of DZD9008; SAE is required to be collected from inform consent ьio

^{*:} Day 1 of Cycle 2, 3, 4

- h. For CID1, -1 day window is allowed for laboratory safety testing and physical examination
- Eye examination includes: Visual acuity, Pupils, Intraocular pressure, External examination, Slit-lamp examination, and Fundoscopic examination (pupil dilate is not required) and others if clinically indicated. . _:
- PRO-CTCAE and FACIT GP5 questionnaire will be collected weekly for the first 18 weeks (to cycle 6), and then on day 1 of each subsequent cycle (expansion cohort 3-6).

Table 14 Study Plan of Part B Dose Extension

Assessment	Screen		Cycle 1 (21 days)		Cycle 2 (21 days) onwards	Discontinuation	28-day follow up	Details in section
Day	-28 to -1	1 h	8a	15ª	1^{b}			
Informed consent	X							4.1.1
Demography & baseline characteristics	X							6.3.1
Medical/surgical history	X							6.3.1
Inclusion/exclusion criteria	X							4.1
Physical examination	X	X			X	X		6.3.2
ECOG performance status	X	X			X	X		6.3.2
Brain MRI or contrast enhanced CT	X							4.1
Pregnancy test (premenopausal females only)	Χ°					X		6.3.4
Ophthalmology assessment i	X					X		6.3.5.4
Archival tumor tissue or fresh biopsy (mutation confirmation and/or companion diagnostics development) ^m	X							6.6.1
Vital signs	X	X	X	X	X	X		6.3.3
Height	X							6.3.3
Weight	X	X			X	X		6.3.3
ECG	X	X##	X	X	X##	X		6.3.5
Clinical chemistry/ Hematology/Urinalysis	X	X	X	×	X	X		6.3.4
HBV/HCV/HIV/COVID-19 ^d	X							4.2

Clinical Study Protocol Drug Substance: DZD9008 Protocol No.: DZ2019E0001 Edition Number: 12.0 Date: July 24,2023

Assessment	Screen		Cycle 1 (21 days)		Cycle 2 (21 days) onwards	Discontinuation	28-day follow up	Details in section
Day	-28 to -1	1 h	8 _a	15ª	1b			
APTT/INR	X	X	X	X	X	X		6.3.4
Echocardiogram/MUGA °	X	····	On	Cycle 3 L	On Cycle 3 Day 1, then every 6 weeks	← s		6.3.5.2
Lung function test (LFT) ^e	X	→	On	Cycle 3 1		←s>		6.3.5.3
EQ-5D-5L		X	Every	6 weeks 1	Every 6 weeks relative to first dose	X		6.9.1
PRO-CTCAE and FACIT GP5 questions		X	X	X	Weekly until the end of cycle 6, than on day 1 of each cycle	×		6.9.2 & 6.9.3
PK blood samples ¹		X	X	X	X			6.5.1.3
Paired tumor biopsy (Subject joins PoM study only)	×				X (C2D1)			6.6.2.2
Plasma sample for the development of Iiquid biopsy companion diagnostic	X							6.6.1
Blood sample for ctDNA & exploratory Biomarkers (optional)		X	X	X	X (C2D1-C6D1 and continuous every odd cycle D1 until disease progression)	ontinuous every odd cy progression)	cle D1 until disease	6.6.2.3
Blood sample for pharmacogenetics (optional)		ίΧ						6.6.3
RECIST assessments ^f	X		·····-	O	On Cycle 3 Day 1, then every 6 weeks	ery 6 weeks	^	6.8.1
Dose with DZD9008			·	XX	X (daily dosing)	+		5.1.4
Concomitant medication		→			X	←X	+	4.3.1
Adverse events g		·····			X		+	6.4
Survival status ^k	·	····			X	←X	+	6.3.6.3

##: multiple time points for ECG. Refer to section 6.3.5.1 for details.

- *: Day 1 of Cycle 2, 3, 4
- a. ± 1 -day visit window is allowed for C1D8 & D15.
- All study visits from Cycle 2 Day 1 onwards may be performed within a visit window of ± 2 days. Survival follow up may be performed within a visit window of ± 7 Ъ.
- Pregnancy test needs to be within 7 days of the first dosing. For Italy only: additional tests at pre-dose on Day 1 of Cycle 2 and each subsequent cycle, as clinically indicated, and during the safety follow-up period (2 weeks \pm 3 days after the last dosing) ပ
- d. HBV/HCV/HIV/COVID-19 test can be done based on local practice.
- e. Echo/MUGA and LFT needs to be done within 14 days of the first dosing.
- It is suggested that site to conduct the first tumor assessment no earlier than C3D1 (±7days). CT is preferred for extracranial tumor. Same scan modality is required to use for tumor scan and RECIST assessment from baseline till follow up for one patient. Please refer to Appendix F of CSP about the details of RECIST assessment. ij.
- AE will be collected from the first dosing of DZD9008 and SAE is required to be collected from inform consent ьio
- h. For C1D1, -1 day window is allowed for laboratory safety testing and physical examination
- Eye examination includes: Visual acuity, Pupils, Intraocular pressure, External examination, Slit-lamp examination, and Fundoscopic examination (pupil dilate is not required) and others if clinically indicated.
- If for any reason the sample is not drawn prior to first dose (pre-dose at C1D1) it may be taken at any visit until the last study visit.
- Survival status including anti-cancer therapy will be collected every 6 weeks following disease progression or withdrawal from treatment. ۲.
- there is a dose interruption, dose reduction, or an early termination due to an AE, or there is an SAE, the investigator may choose to collect an unplanned blood sample (if Multiple time point for PK sampling on C1D1 and C3D1, details refer to Table 8 and Table 9. Hospitalization can be allowed for out of business time PK collection. If possible) within the 24 hour after the last dose.
- Adequate amounts of archived tumor tissue or fresh biopsy (if archived tissue is not available) will be collected for Sponsor designated central laboratory confirmation of EGFR Exon20ins mutations. If a pre-study written documentation of EGFR Exon20ins in tumor tissue is available from Sponsor designated central laboratory using the designated assay, no additional tumor sample needs to be submitted. Requirements of tumor tissue sample collection can be referred to the Laboratory Manual. ij.

Lab visits and clinical monitoring (Part A, dose escalation)

Table 15

Measurement	Scr	Screening	ŭ	C0D1	ວ	CIDI	C	C1D8	C	C1D15	C	C2D1	C2D8	86	C2D15	w	C3D1		C4 & C5 onwards D1		End of treatment	
		Blood Vol.		Blood Vol.		Blood Vol.		Blood Vol.		Blood Vol.		Blood Vol.	B	Blood Vol.	Blood Vol.	Blood Vol.	Blood Vol.	p .	Blood Vol.	р.	Blood Vol.	od ol.
Hematology	×	4ml	×	4ml	×	4ml	×	4ml	X	4ml	x	4ml				×	4ml	×	4ml	×	4ml	뎔
Clinical chemistry	×	4ml	×	4ml	×	4ml	×	4ml	X	4ml	x	4ml				×	4ml	×	4ml	×	4ml	뎔
APTT/INR	×	4ml	×	4ml	×	4ml	×	4ml	×	4ml	×	4ml				×	4ml	×	4ml	×	4ml	딥
HBV, HCV, HIV screening	×	6ml																				
Urinalysis	×		×		×		×		×		×		×		×	*		×		×		
Pregnancy Test (Urine)	×																			×		
Plasma PK Pre			×	4ml	×	2ml	×	2ml	x	2ml	x	4ml				×	2ml	×	2ml	_		
Plasma PK 0.5h post			x	4ml							х	4ml										
Plasma PK 1h post			х	4ml							х	4ml										
Plasma PK 2hr post			×	4ml							x	4ml										
Plasma PK 3hr post			х	4ml							х	4ml										
Plasma PK 4hr post			×	4ml							×	4ml										
Plasma PK 6hr post			x	4ml							х	4ml										
Plasma PK 8hr post			×	4ml							Х	4ml										
Plasma PK 10hr post			х	4ml							x	4ml										
Plasma PK 12hr post			x	4ml							х	4ml										
Plasma PK 24hr post			×	4ml							×	4ml°										
Plasma PK 48hr post			x	4ml																		
Plasma PK 72hr post			х	4ml																		
Plasma PK120hr post			х	4ml																		

Measurement	Scr	Screening	S	C0D1	C	CIDI	C	C1D8	5	C1D15	Ü	C2D1	C2D8		C2D15) 	C3D1	C4 onw	C4 & C5 onwards D1	En	End of treatment
		Blood Vol.		Blood Vol.		Blood Vol.		Blood Vol.		Blood Vol.		Blood Vol.	Blood Vol.	ъ.	Blood Vol.		Blood Vol.		Blood Vol.		Blood Vol.
Plasma PK168hr post			×	4ml																	
Urine PK											р×										
4-β- hydroxycholesterol / total cholesterol			×	6ml	x	6ml	×	6ml	X	6ml	x	6ml									
Blood sample for ctDNA & Exploratory Biomarker	×	10ml	×	10ml	×	10ml	×	10ml	×	10ml	×	10ml				× 10	x 10ml (C3-C6 D1 and continuous every even cycle D1 afterwards) ^b	36 D1 s	(C3-C6 D1 and continuous even cycle D1 afterwards) ^b	nuous trds) ^b	every
BP/HR	Х		X a		X a		X a		X a		Х					х		x		x	
ECG	×		x a		x a		x a		_e X		×					×		×		×	

a: time point: pre-dose, 1, 2, 4, 6, 10, 24 hours post dose. The 24 hours' time point falls on the 2nd day.

b: detailed time points see Section 6.6
c: 24hr post dosing should be collected before dosing on C2D2
d: The interval for urine collection on cycle 2 day 1 are 0-4, 4-12, and 12-24 hours. Next dosing on C2D2 should be given after the urine collection.

Lab visits and clinical monitoring (Part A dose expansion) Table 16

Parameters	Ser	Screening	CIDI	10	5	C1D8	C1D15	315		C2D1	S	C3D1	C4	C4 onwards D1	E	End of treatment
		Blood Vol.		Blood Vol.		Blood Vol.		Blood Vol.		Blood Vol.		Blood Vol.		Blood Vol.		Blood Vol.
Hematology	×	4ml	Х	4ml	×	4ml	×	4ml	x	4ml	X	4ml	×	4ml	X	4ml
Clinical chemistry,	x	4ml	X	4ml	×	4ml	×	4ml	x	4ml	Х	4ml	X	4ml	X	4ml
APTT/INR	x	4ml	х	4ml	×	4ml	×	4ml	×	4ml	×	4ml	×	4ml	×	4ml
HBV, HCV, HIV screening	×	6ml														
Urinalysis	×		x		×		×		×		×		×		×	
Pregnancy Test (Urine)	×														×	
Plasma PK Pre			×	2ml	×	2ml	×	2ml	×	2ml	×	2ml	×	2ml (only C4)		
Plasma PK 0.5hr Post			х	2ml					×	2ml						
Plasma PK 1hr Post			x	2ml					×	2ml						
Plasma PK 2hr Post			X	2ml					x	2ml						
Plasma PK 3hr Post			Х	2ml					x	2ml						
Plasma PK 4hr Post			x	2ml					×	2ml						
Plasma PK 6hr Post			Х	2ml					×	2ml						
Plasma PK 8hr Post			X	2ml					x	2ml						
Plasma PK 10hr Post			Х	2ml					x	2ml						
Plasma PK 12hr Post			X	2ml					×	2ml						
Plasma PK 24hr Post			Х	2ml ^b					×	2ml°						
Blood sample for ctDNA & Exploratory Biomarker	×	10ml	x pre- dose	10ml	×	10ml	×	10ml	×	10ml	x 1	Jml (C3-	C6 D1 cycle I	x 10ml (C3-C6 D1 and continuous every even cycle D1 afterwards)*	ous eve s)ª	ry even
BP/HR	x		x d		p X		p X		x		х		X		X	
ECG	×		p X		p X		pX		×		×		×		×	
a. datailed time nointe coe Coetion 6 6																

a: detailed time points see Section 6.6

^b: 24hr post dosing should be collected before dosing on C1D2
^c: 24hr post dosing should be collected before dosing on C2D2
^d: time points: pre-dose, 1, 2, 4, 6, 10, 24 hours post dose. The 24 hours' time point falls on the 2nd day.

Lab visits and clinical monitoring (Part A, food effect)

Table 17

							Cycle 0	0						ي.	Cycle 1		Cy	Cycle 2 & onward	rd
	Scree	10	D2	D3	D4	9Q	D8	60	D10	D111	D12 I	D14 D	D16 C1D1		C1D8	C1D15	C2D1	C3D1 and onward	End of study
Plasma PK Pre		2 ml						2 ml									2 ml		
Plasma PK 0.5hr post		2 ml						2 ml											
Plasma PK 1hr post		2 ml						2 ml											
Plasma PK 2hr post		2 ml						2 ml											
Plasma PK 3hr post		2 ml						2 ml											
Plasma PK 4hr post		2 ml						2 ml											
Plasma PK 6hr post		2 ml						2 ml											
Plasma PK 8hr post		2 ml						2 ml											
Plasma PK 10hr post		2 ml						2 ml											
Plasma PK 12hr post		2 ml						2 ml											
Plasma PK 24hr post			2 ml						2 ml										
Plasma PK 48hr post				2 ml						2 ml									
Plasma PK 72hr post					2ml						2 ml								
Plasma PK 120hr post						2 ml					7	2 ml							
Plasma PK 168hr post							2 ml					2	2 ml						
Pregnancy test	×																		
Hematology	4 ml	4 ml											4	4 ml			4 ml	4 ml	4 ml
Clinical chemistry	4 ml	4 ml											4	4 ml			4 ml	4 ml	4 ml
Blood sample for ctDNA & Exploratory Biomarker	10ml	10ml											10	10ml 10	10ml	10ml	× 10 ₁ continu	× 10ml (C2-C6 D1 and continuous every even cycle D1 afterwards) ^b	n cycle
BP/HR		X^a	\mathbf{x}^{a}					x _a	Xa				×	\mathbf{x}^{a}	xa	Xa	Х	Х	x
ECG		X^a	X _a					Xa	Xa				*	X _a	Xa	X _a	х	х	×
HBV/HCV/HIV	6 mL																		

							Cycle 0	0							Cycle 1		Cy	Cycle 2 & onward	rd
	Scree	1Q	D2	D3	D4	9Q	D8	D9	D10	D111	D12	D14	D16 (CIDI	C1D8	C1D15	C2D1	C3D1 and onward	End of study
APTT/INR	4 ml	4 ml												4 ml			4 ml	4 ml	4 ml

a: time point: pre-dose, 1, 2, 4, 6, 10, 24 hours post dose. The 24hour time point falls on the 2nd day. b. detailed time points see Section 6.6

Table 18 Lab visits and clinical monitoring (Part B dose extension)

Parameters	Scr	Screening	D C1	CIDI	C	C1D8	[L]	CID15	Ö	C2D1	Ö	C3 D1	C4 (C4 onwards D1	E tres	End of treatment
		Blood Vol.		Blood Vol.		Blood Vol.		Blood Vol.		Blood Vol.		Blood Vol.		Blood Vol.		Blood Vol.
Hematology	×	4ml	×	4ml	×	4ml	×	4ml	×	4ml	×	4ml	×	4ml	×	4ml
Clinical chemistry,	×	4ml	×	4ml	×	4ml	×	4ml	x	4ml	×	4ml	×	4ml	×	4ml
APTT/INR	×	4ml	×	4ml	×	4ml	×	4ml	x	4ml	×	4ml	×	4ml	×	4ml
HBV, HCV, HIV, COVID-19 screening	×	6ml														
Urinalysis	×		×		×		×		×		×		×		×	
Pregnancy Test (Serum/ Urine)	р×														×	
Plasma PK Pre			×	2ml#	×	2ml#	×	2ml#	×	2ml#	х	2ml#	x	2ml# (C5, C7, C9 and C11)		
Plasma PK 1hr Post			×	2ml*							×	2ml*				
Plasma PK 2hr Post			×	2ml*							×	2ml*				
